Power for the study is based on the primary outcome of proportion of VS in children in the intervention vs. control arms at 12 months after enrollment for each child (Aim 1). We estimated requiring a sample size of 90% (630) of an estimated 700 children eligible to enroll to have 80% power to detect an effect size of a difference between arms of at least 11%. Accounting for 10% loss to follow-up over 12 months, this sample size is expected to provide total of 567 children (or 284 per arm) with outcomes for analysis. These calculations are based on Fisher's exact test, two-sided $\alpha=0.05$, and initial VS rates of approximately 65% (estimated from historical facility data).

Table 5: Effect sizes and power calculations				
VS rates, control (SOC) vs. intervention (POC) arms	Difference (effect size)	Power	Expected Total N for analysis	Expected N per arm for analysis
65% vs. 70%	5.0%	0.22	567	284
65% vs. 72.5%	7.5%	0.45	567	284
65% vs. 75%	10%	0.71	567	284
65% vs. 76%	11%	0.80	567	284
65% vs. 77.5%	12.5%	0.89	567	284
65% vs. 80%	15%	0.98	567	284
70% vs. 80%	10%	0.76	567	284
70% vs. 82.5%	12.5%	0.93	567	284
70% vs. 85%	15%	0.99	567	284

A power calculation was also performed for how precisely the prevalence of DRMs could be estimated. With 284 participants randomized to the intervention arm, we expected approx. 35% (100) to not achieve VS at their 1st POC VL test and undergo DRM testing, and we would be able to estimate prevalence of DRMs to within +/- 5% to 10% of the 95% CIs. For example, for a class of DRMs with prevalence of 80%, we anticipate generating exact 95% CIs of 71.3%-87.0%; a less common DRM at 10% will generate 95% CIs of 5.1%-17.1%.

Outcome Variables

Aim 1 primary outcome

Our study's primary outcome is the child's VS (defined as $VL < 1000$ copies/mL) at 12 months after enrollment (defined as from a blood draw within 12 months +/- 16 weeks after the enrollment date). VL quantity is determined using results from the study's POC HIV VL GeneXpert test result which was planned for both randomization groups at the 12-month time point. Where a participant has no POC result available at 12 months but does have a standard laboratory VL available at 12 months, the standard laboratory VL is used. A month is considered to be 28 days.

Aim 1 VL sensitivity analysis outcomes

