VS outcomes for sensitivity analyses of our primary comparison are the same as the primary VS outcome but use lower VL cutoffs of suppression (<40 copies/mL, which was the lower limit of detection for both the study POC and some standard lab-based VL assays, and <400 copies/mL, which is the operational VS threshold at which clinical management for potential non-VS changes based on updated Kenyan and WHO guidance).

Aim 1 Secondary outcomes

Secondary study outcomes for Aim 1 include process outcomes used to understand implementation of POC VL testing; these are:

- Uptake, defined as whether the study POC VL test was performed at the study visits (intervention group only)
- Turn-around time for the VL testing results at each study visit (intervention group, and if available, SOC group)
- Retention in care (both groups)
- ART switches (both groups)

Aim 2 outcomes

The study DRM testing outcomes include:

- Frequency of DRM test being performed, among tests at which child is not virally suppressed (test result of $VL \geq 1000$ copies/ml)
- Frequency and proportion of DRM tests showing any major DRM: major mutations within each class of HIV drugs, e.g., NRTIs, NNRTIs, and PIs.
- Among children tested for DRM,
 - frequency recommended to change regimens
 - among those recommended to change, frequency who actually did so by month 12.

Exposure Variables

Consistent with principles of intent-to-treat analysis (ITT), the primary exposure in this trial is randomly assigned intervention group. Children are analyzed in the group to which they were randomly assigned regardless of post-randomization events, such as the caregiver or child refusing the intervention, or a child being allocated in practice to the incorrect arm.

General statistical considerations

Binary variables will be described with frequency and proportion (as a percentage); continuous outcomes will be described with median (IQR), with IQR represented as (Q1, Q3). Statistical testing will be at the 0.05 significance level ($\alpha=0.05$).

Missing Data

Analyses will be complete case analysis, meaning we will not impute VL outcomes for participants who do not contribute an observed VL measurement at 12 months.

Statistical Analyses

Enrolled population:

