While not our primary outcome, interim descriptive statistics of VLs over time are provided for VS at baseline and quarterly thereafter. For participants in the POC group, POC test results are used. For participants in the SOC group, SOC test results are used. Testing over time is shown descriptively using testing intervals defined by days since enrollment: Enrollment = 0-2 years prior to enrollment; 3 months = 1 day to 3 months + 6 weeks after enrollment; 6 months = 6 months +/- 6 weeks; 9 months = 9 months +/- 6 weeks. This could differ from study visits as assigned by visit staff, for example if a 6 visit was attended over 6 weeks late it could fall in the 9-month interval. If more than one test had been performed in an interval, the test closest to the target date is used.

Study Aim 1. Effect of the intervention:

All analyses of the effect of the intervention are ITT, using randomized group assignment as the exposure variable as described in the Exposure Variables section (p3).

Aim 1a: We hypothesize that the proportion with VS one year after enrollment will be higher among children randomized to POC VL testing compared to those in the control group. Our primary analysis will compare the proportion of children with VS 12 months after enrollment as defined by our primary outcome in the intervention vs. control groups, estimating the RR for the intervention effect using a modified Poisson regression model with robust standard errors, adjusting for facility and age group strata (1-9 or 10-14 years). We provide supporting descriptive statistics of the primary outcome by randomized group. Sensitivity analyses using lower cutoffs for VS follow the same methods as the primary analysis except outcomes are as specified for sensitivity analyses of the primary outcome; they present an *a priori* sensitivity analysis comparing VS at 12 months defined as <40 copies/mL. A *post hoc* sensitivity analysis defines VS at 12 months as <400 copies/mL.

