POC group was not consistently performed quarterly due to COVID interruptions either delaying or preventing in-person visits, especially at study months 6 and 9. Also, for SOC children, the routine testing schedule did not necessarily align with study enrollment, resulting in SOC VLs performed at enrollment only for a subset of SOC children, and subsequently, SOC was not necessarily performed quarterly. Because in neither arm was time to VS measured consistently, we changed from comparing time to VS by estimating a hazard ratio from Cox regression, to comparing VS at 12 months by estimating a relative risk from a modified Poisson regression so that our outcome is measured in the same manner in both groups. Second, because in SOC only a subset were tested at enrollment, we used first VL test up to and including 6 months to identify SOC children who were initially unsuppressed. Third, we defined the cutoff for being initially unsuppressed and for achieving VS after enrollment to be based on 40 copies/mL to allow us to explore the question of value of our intervention in those not clearly initially suppressed. After unblinding, we discovered that enrollment VL data in those with both POC and SOC tests showed that POC tests missed a noticeable number of those with $VL > 40$ by SOC, but not in those with $VL > 400$ copies/mL; to reduce any bias from differences in the tests we changed our plan to use a cutoff of 400 copies/mL both for identifying initially unsuppressed children and for the VS outcome at 12 months for this analysis.

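### The a priori <40 copies/mL sensitivity analysis for Aim 1a can mix POC and laboratory results that the SAP itself found to disagree at 40, with no POC-only check and no report of assay source by arm

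*SAP*

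**What the plan says.** The primary outcome (SAP, Aim 1 primary outcome) is suppression below 1000 copies/mL on the study POC test, planned at 12 months for both arms. If a child has no POC result in the window but does have a laboratory one, "the standard laboratory VL is used". The window is 12 months ± 16 weeks, with a month of 28 days.

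The lower-cutoff outcomes (SAP, Aim 1 VL sensitivity analysis outcomes) differ from the primary outcome only in the cutoff, so they keep this fallback. That section describes 40 copies/mL as the value "which was the lower limit of detection for both the study POC and some standard lab-based VL assays". Under Study Aim 1, Aim 1a, the SAP lists an a priori "sensitivity analysis comparing VS at 12 months defined as <40 copies/mL" and a post hoc version at <400.

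Under Changes to the analysis plan, the authors report that, among children with both tests at enrolment, the data "showed that POC tests missed a noticeable number of those with" a laboratory value above 40, but that this was not so above 400. They therefore moved Aim 1b to 400, both for defining initially unsuppressed children and for the 12-month outcome. Aim 1b otherwise uses the primary outcome's definition.

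**The concern.** Aim 1a at <40 and the former Aim 1b outcome at <40 share one construction: the same window, the same POC-first rule and the same laboratory fallback. The SAP judged that construction open to bias from assay differences in Aim 1b and changed it. It left the construction at 40 in Aim 1a with no caveat, no POC-only run and no count of which assay supplied the result in each arm.

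If the arms differ in how often the laboratory result is used, part of any difference at <40 reflects the assay rather than the child. The <40 analysis is the only lower-cutoff analysis labelled a priori, so readers are likely to take it as the prespecified robustness check. There is a second gap. If 40 is the limit for only some laboratory assays, the SAP needs a rule for below-limit results from the others, and it gives none.

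**Working it through.** **The plan's own figure.** The documents give no expected rate, effect or power at <40. Their only related calculation is the power table, for <1000 copies/mL. "These calculations are based on Fisher's exact test, two-sided" α = 0.05, with 284 per arm (700 × 0.9 × 0.9 = 567; 567 / 2 = 283.5). Exact enumeration gives 0.799 for 65% vs 76%, against the stated 0.80, and all nine rows reproduce within 2 points. The table is sound but says nothing about the <40 analysis.

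**Bias formula, assuming no true effect.** For each arm let
- T = proportion below 40 by laboratory,
- m = share of children at or above 40 by laboratory but below 40 by POC,
- f = share of 12-month outcomes supplied by laboratory fallback.

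The observed proportion below 40 is T + (1 − f) × m. With T and m equal across arms and fallback unrelated to viral load, the spurious risk difference (intervention − control) is

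(1 − f_I) × m − (1 − f_C) × m = m × (f_C − f_I).

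T cancels. Disagreement in the other direction would make m a net share; the SAP reports only the direction used here.

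**Inputs.** The documents give no value for m, f_I or f_C. All values below are assumptions. Results are in percentage points.

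| Fallback, intervention / control | m = 2% | m = 5% | m = 10% | m = 15% |
|---|---|---|---|---|
| 0% / 10% | +0.2 | +0.5 | +1.0 | +1.5 |
| 0% / 20% | +0.4 | +1.0 | +2.0 | +3.0 |
| 5% / 20% | +0.3 | +0.75 | +1.5 | +2.25 |
| 0% / 40% | +0.8 | +2.0 | +4.0 | +6.0 |
| 10% / 10% | 0 | 0 | 0 | 0 |
| 20% / 5% | −0.3 | −0.75 | −1.5 | −2.25 |

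For example, 0.15 × (0.40 − 0) = 0.060 and 0.15 × (0.05 − 0.20) = −0.0225. The planned estimand is a relative risk, which does need T. Taking T = 0.65 purely for illustration (the plan's 65% refers to <1000), these extremes become 0.80 / 0.74 = 1.081 and 0.77 / 0.7925 = 0.972.

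**Is fallback likely to differ by arm?** The window is 12 × 28 = 336 days ± 112, that is days 224 to 448.
- Quarterly POC draws over the first 12 months (Protocol, Procedures) put month 9 (day 252) and month 12 (day 336) inside the window for the intervention arm.
- Control children have one planned POC test in it, at month 12 (Protocol, Study methods).
- The SAP gives routine laboratory testing as six-monthly, about 168 days. The window spans 224 days, so a control child tested on schedule would have a laboratory result to fall back on.
- Against this, the SAP's change log says COVID disrupted POC visits in the intervention arm, especially at months 6 and 9.

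**The case against.** A reader might infer that fallback falls mainly in the control arm, so that the analysis is tilted toward the intervention. The documents do not support that as a fact. POC at 12 months was planned for every child in both arms, the fallback rule is the same for both, and no fallback counts are given. The extra month-9 draw makes more fallback in control plausible, but that is one of the visits COVID disrupted most.

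Other objections have weight:
- The disagreement was seen in enrolment data. Its size and the interval between paired tests are not stated, so it may not carry over to 12 months.
- In Aim 1b, assay differences also affected who entered the analysis, because initial status was set by POC in one arm and by the first test up to 6 months in the other. The case for changing the cutoff was stronger there. This does not remove the inconsistency, because the SAP moved the 12-month outcome as well.
- Saying that laboratory results with a limit other than 40 cannot be classified goes too far: the SAP does not say those limits are higher. If some are, and below-limit results count as suppressed, the effect would favour whichever arm has more fallback, opposite to the assay-sensitivity effect.
- Aim 1a also has a <400 analysis, at a level where the SAP reports no such problem, and assay agreement is to be reported down to <40. Both help a reader, but neither shows which assay supplied the 12-month result in each arm.

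**Conclusion.** The point holds as an internal inconsistency with a conditional bias. The a priori <40 analysis can mix assays that the SAP reports as disagreeing at 40, and the SAP acted on that in Aim 1b but not in Aim 1a. The bias favours the intervention if fallback is more common in control, is zero if the shares are equal, and reverses otherwise. Over the assumed inputs it runs from −2.25 to +6.0 points. That range illustrates the formula and does not estimate the bias, since m and both fallback shares are unknown from the documents. The issue is confined to one sensitivity analysis. A reader might extend it to the primary result, but the SAP reports no disagreement above 400, and nothing shows the <1000 comparison to be affected.

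**What to change.** 1. Tabulate the assay source of the 12-month result (POC or laboratory) by arm.
2. Keep the planned <40 analysis and add a supplementary <40 analysis restricted to POC results, which makes the assay-mixing term zero by construction.
3. State how laboratory results reported below a limit other than 40 are classed. If that limit is above 40, exclude them from the <40 analysis.
4. Interpret the a priori <40 result alongside the POC-only run and the existing <400 analysis.

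The <400 and primary <1000 outcomes should not be replaced by POC-only versions, because the SAP reports no disagreement at those levels.

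The cost is one table, a few sentences in the SAP and one extra run. That run has fewer children, possibly unequally by arm: at an assumed 20% control and 5% intervention fallback it would drop about 57 (0.20 × 284) and 14 (0.05 × 284). Under the SAP's complete-case rule this could introduce a bias of its own, which is why the run should supplement the planned analysis and not replace it.

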Subgroup analyses for the effect of the intervention will examine potential effect modification by age group (1-9 years old or 10-14 years old) using the same model as the primary analysis and including an interaction term between age group and intervention group in the model. While the study is not powered to test the intervention effect within age subgroups, particularly in the subgroup of 10-14 year-olds, this analysis will provide data for the intervention effect within each, as well as for any difference in effect between the younger and older children. Gender, time on ART (< 2 years, 2-5 years, or >5 years), VS status of the caregiver, and whether the caregiver is the biological parent are also *a priori* subgroup variables considered for effect modification, in each case by adding the main effect of the subgroup variable and the interaction term between subgroup variable and randomization group.

Aim 1b: we hypothesize that among children newly initiating ART or initially unsuppressed, the proportion with VS one year after enrollment will be higher among children randomized to POC VL testing compared to those in the control group. The analysis among children newly initiating ART or initially unsuppressed will follow the same methods as the primary analysis to compare the proportion of children with VS 12 months after enrollment as defined by our primary outcome except that VS will be defined as <400 copies/mL and the analysis will be limited to the population of children meeting our definition of newly initiating ART or initially unsuppressed. Children newly initiating ART are defined as those initiating ART within 30 days of study enrollment. Children initially unsuppressed are those with VS ≥ 400 copies/mL. for the POC group, at the initial POC VL test. Because in SOC only a subset were tested at enrollment, we used first VL test up to and including 6 months to identify SOC children who were initially unsuppressed (i.e., from enrollment testing interval to 6 month testing interval).

Subgroup analyses for the effect of the intervention among children newly initiating ART or initially unsuppressed are conducted for subgroups defined by age group, and for subgroups defined by children newly initiating ART vs. those already on ART but initially unsuppressed. For each, the effect of the intervention within subgroups is estimated by including the appropriate main effect and interaction term in the model.

Other associations with VS

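### SAP Aim 1b picks its initially unsuppressed children by a different rule in each arm, so its risk ratio can move off 1 in either direction without any intervention effect

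*SAP*

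**What the plan says.** **Entry rules (SAP, Study Aim 1, Aim 1b).** The cut-off is 400 copies/mL in both arms. The test it is applied to differs. Entry is decided "for the POC group, at the initial POC VL test". For the SOC arm, "we used first VL test up to and including 6 months to identify SOC children who were initially unsuppressed".

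**Intervals (SAP, VLs over time).** "Enrollment = 0-2 years prior to enrollment; 3 months = 1 day to 3 months + 6 weeks after enrollment". The 6-month interval is 6 months plus or minus 6 weeks, and the SAP counts a month as 28 days. Within an interval, "If more than one test had been performed in an interval, the test closest to the target date is used".

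**Timing of the first POC test (Protocol, Study methods, Aims 1 & 2).** For children already on ART it is scheduled three months after their last VL, or at the next visit if they have never had one.

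**Estimates affected.** These are the pooled Aim 1b RR and the planned analysis "for subgroups defined by children newly initiating ART vs. those already on ART but initially unsuppressed". The model is the modified Poisson regression of the primary analysis, adjusted for facility and age group.

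**Disclosure (SAP, Changes to the analysis plan, Study Aim 1b).** The SAP gives its reason: "the routine testing schedule did not necessarily align with study enrollment", so only some SOC children had a VL at enrolment. It dates this change before unblinding. The move of the cut-off from 40 to 400 came after unblinding and is explained by disagreement between the assays.

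**The concern.** Randomisation makes the arms comparable. It does not make two subsets comparable when each is picked by its own rule, and here part of the picking uses tests taken after randomisation. Two mechanisms pull in opposite directions:

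- **Late SOC tests raise the RR.** A SOC child with no earlier VL who is unsuppressed at enrolment but re-suppresses before the first test never enters the SOC set. The SOC children who do enter late have less time left in which to re-suppress by month 12. POC looks better.
- **Old SOC tests lower the RR.** A SOC child classified on a test from months before enrolment may already have re-suppressed by enrolment. SOC looks better.

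If the first POC test falls after enrolment, the first mechanism works in the POC arm too and pulls the RR down.

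Changing Aim 1b from time to suppression to a 12-month endpoint made the outcome comparable across arms but left entry unequal. The SAP plans no analysis under a common entry rule. At stake is whether a difference, or its absence, among the children the intervention is aimed at can be read as an effect of the intervention.

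**Working it through.** **The plan's own figures.** The documents state no size, power or bias figure for Aim 1b. The nearest is the expected number unsuppressed at the first POC test: 0.35 × 284 = 99.4, the SAP's 100. It is used below for pooling.

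**Windows.** SOC classification closes on day 6 × 28 + 42 = 210. The outcome is targeted at day 12 × 28 = 336, with a window of ±112 days (224 to 448).

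**Null model.** It has two states, suppressed and unsuppressed, with identical transitions in both arms, so there is no intervention effect. The Protocol's Preliminary Studies give later suppression of 23% after an unsuppressed VL and 93% after a suppressed one. Taken as 12-month rates:

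- a = 0.23, b = 0.07, π = a/(a+b) = 0.767, λ = 1 − a − b = 0.70
- P(suppressed at day 336 | unsuppressed s × 336 days earlier) = π(1 − λ^s)
- mean for s uniform on (s1, s2): π[1 − (λ^s1 − λ^s2)/((−ln λ)(s2 − s1))]

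| Classifying test | s1 to s2 | P(suppressed at day 336) |
|---|---|---|
| POC at day 0 | 1 | 0.2300 |
| POC uniform over days 0–84 | 0.75 to 1 | 0.2053 |
| SOC uniform over days 0–210 | 0.375 to 1 | 0.1655 |
| SOC uniform over prior 182 days | 1 to 1.542 | 0.2787 |
| SOC uniform over prior 365 days | 1 to 2.086 | 0.3217 |

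The lags of 182 and 365 days mirror the routine schedules in the SAP (six-monthly) and the Protocol (annual). The 84-day POC spread and the share w of SOC tests after enrolment are assumptions.

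**Subgroup already on ART.** Null RR = P(POC) / [(1 − w) × P(prior) + w × 0.1655].

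| POC test | SOC prior lag | w = 0.25 | w = 0.50 | w = 0.75 | RR = 1 at w |
|---|---|---|---|---|---|
| day 0 | 365 | 0.81 | 0.94 | 1.12 | 0.59 |
| day 0 | 182 | 0.92 | 1.04 | 1.19 | 0.43 |
| days 0–84 | 365 | 0.73 | 0.84 | 1.00 | 0.74 |
| days 0–84 | 182 | 0.82 | 0.92 | 1.06 | 0.65 |

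Example, first cell: the SOC mean is 0.25 × 0.1655 plus 0.75 × 0.3217, which is 0.2827, and 0.2300 divided by 0.2827 is 0.81. Break-even in that row: 0.3217 minus 0.2300 is 0.0917, 0.3217 minus 0.1655 is 0.1562, and 0.0917 divided by 0.1562 is 0.59.

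**Pooled Aim 1b.** Assume 100 unsuppressed children per arm, plus 12 newly initiating per arm (half of the Protocol's 24) at an assumed 65% suppressed. Each p becomes (7.8 + 100p)/112.

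- POC at day 0: POC is 0.275, and the range is 0.85 to 1.13.
- POC over days 0–84: POC is 20.53 plus 7.8, divided by 112, which is 0.253. The SOC extremes are 28.27 plus 7.8, divided by 112, which is 0.322, and 19.38 plus 7.8, divided by 112, which is 0.243, giving 0.79 to 1.04.

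**Sensitivity to a.** With POC at day 0, the subgroup range of 0.81 to 1.19 narrows to 0.88 to 1.17 if 12-month re-suppression is 0.50, and to 0.94 to 1.14 if it is 0.70.

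**Scale.** With 112 per arm at 27.5% suppressed, SE(log RR) = √(2 × 0.725 ÷ (112 × 0.275)) = 0.217. The 95% limits are a factor exp(1.96 × 0.217) = 1.53 either way. The bias would shift the estimate rather than swamp it, but the confidence interval does not reflect the shift.

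**Common rule.** Simulating the same model with one pre-enrolment test 0 to 2 years back in both arms gives 39.0% versus 39.0% suppressed, a null RR of 1.00.

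**The case against.** **Disclosed, and set before unblinding.** Both are true of the SOC rule. That answers a worry about data-driven choice; it does not make the two sets comparable. The post-unblinding move to 400 concerns assay agreement, not timing.

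**The numbers rest on assumptions.** This stands. The transition rates are historical and use a cut-off of 1000. The 23% came from follow-up VLs at a mean of 11.3 months. The result is sensitive to when the POC test fell: spreading it over days 0–84 removes most of the upward bias. The SAP mentions enrolment results in children with both POC and SOC tests, so some POC tests were done at enrolment, but the mix is unknown. A high share of SOC tests after enrolment also sits awkwardly with short prior lags, since the first needs poor routine testing and the second good routine testing.

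**It is a secondary analysis.** This also stands. The Protocol's Data Analysis Plan treats it so, and power and the primary outcome belong to Aim 1a. A reader might infer from the SAP's Study Objectives that this comparison is part of the leading objective. What is placed there as Aim 1b is time to suppression, the Cox analysis since replaced.

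**Intention to treat.** A reader might say the ITT label is false. The SAP writes "All analyses of the effect of the intervention are ITT, using randomized group assignment as the exposure variable" and "Children are analyzed in the group to which they were randomly assigned regardless of post-randomization events". Aim 1b does analyse children by assigned arm, so it meets that definition. The problem is how the subgroup is formed.

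**Conclusion.** The point holds at moderate weight. The entry rule differs by arm. SOC entry can fall long before or well after randomisation, and POC entry may also come after it. The Aim 1b RR, and more so the RR for children already on ART but initially unsuppressed, can differ from 1 with no intervention effect. Under the stated assumptions (25 to 75% of SOC tests after enrolment, the rest over the prior 182 or 365 days) the subgroup null RR lies at about 0.81 to 1.19 with POC tests at day 0 and about 0.73 to 1.06 with POC tests over days 0 to 84. The true size and sign cannot be had from the documents, and the two mechanisms may nearly cancel.

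Two stronger readings are tempting. One is that the rule favours POC; the model gives either sign, depending on dates not reported. The other is that no causal statement about this subgroup is permissible; a bias of unknown size and sign, which may be near zero, supports caution and a check, not a ban. Aim 1a and the 30-day rule for newly initiating children are untouched.

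**What to change.** 1. Add an Aim 1b sensitivity analysis, labelled post hoc because this analysis is already unblinded. In both arms take the most recent routine VL on or before enrolment within the SAP's 0 to 2 year window and apply the 400 cut-off to the recorded value. Keep newly initiating children as now defined. Apply the same rule to the subgroup already on ART.
2. Report by arm how many children have no prior VL, and the dates of the classifying tests relative to enrolment in both arms.
3. Describe the current-rule result as exploratory, because its analysis sets were not defined by a common baseline rule, and interpret it beside the common-rule result.

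The cost is SAP wording, one derived flag and additional model fits, with no new data collection. The SAP already lists suppression 0 to 2 years before enrolment as a baseline variable, but its general definition of suppression is below 1000, so the 400 flag needs the underlying VL values.

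The downsides should be stated. An older VL reflects enrolment status less precisely, though by the same rule in both arms. Children without a prior VL drop out in unknown number; the Protocol's Sources of materials section says routine results are recorded unreliably, and plans to supplement them from the national database and facility logs. The target population becomes children unsuppressed at their last pre-enrolment VL. The analysis is itself chosen after unblinding.
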